## 10.2 Off Study Criteria

- a) 100 days after the last dose of the investigational agent (Patients on Part A or C that are not enrolled at the MTD; Patients on Part E).
- b) The fifth anniversary of the date the patient was enrolled on this study (All patients enrolled at the determined MTD)
- c) Death
- d) Lost to follow-up
- e) Withdrawal of consent for any further required observations or data submission.
- f) Enrollment onto another COG therapeutic (anti-cancer) study
- g) Patient did not receive protocol treatment after study enrollment

## 11.0 STATISTICAL AND ETHICAL CONSIDERATIONS

### 11.1 Sample Size and Study Duration

Part A: Phase 1 (single agent) - patients with solid tumors, excluding brain and CNS tumors

Part B: Patients with relapsed or refractory neuroblastoma (B1)

Patients with relapsed or refractory osteosarcoma (B2)

Patients with relapsed or refractory rhabdomyosarcoma (B3)

Patients with relapsed or refractory Ewing Sarcoma or Peripheral PNET (B4)

Patients with relapsed or refractory Hodgkin Lymphoma (B5)  
 Patients with relapsed or refractory Non-Hodgkin Lymphoma (B6)  
 Patients with unresectable melanoma or metastatic melanoma or relapsed melanoma or refractory melanoma (B7)  
 Patients with relapsed or refractory neuroblastoma (MIBG evaluable without RECIST evaluable disease) (B8)

Part C: Phase 1 (combination) - patients with solid tumors, excluding brain and CNS tumors

Part D: Patients with relapsed or refractory neuroblastoma (D1)  
 Patients with relapsed or refractory osteosarcoma (D2)  
 Patients with relapsed or refractory rhabdomyosarcoma (D3)  
 Patients with relapsed or refractory Ewing Sarcoma or Peripheral PNET (D4)  
 Patients with relapsed or refractory Non-Hodgkin Lymphoma (D5)  
 Patients with relapsed or refractory neuroblastoma (MIBG evaluable without RECIST evaluable disease) (D6)

Part E: Patients with relapsed or refractory rhabdomyosarcoma (E3)  
 Patients with relapsed or refractory Ewing Sarcoma or Peripheral PNET (E4)

Part	Minimum	Maximum	Estimated Duration
A	4	36 (20% inevaluable)	2-36 months
B	60	170 (10% inevaluable)	1-2.75 years
C	2	36 (20% inevaluable)	2-36 months
D	0	110 (10% inevaluable)	1-2.75 years
E	2	23 (10% inevaluable)	1-23 months

Part A will enroll a minimum of 2 evaluable patients at each dose level for determination of MTD/Recommended Phase 2 dose (RP2D) of single agent nivolumab. Once the MTD or recommended Phase 2 dose has been defined in Part A, Parts B and C will open concurrently. Part C will enroll a minimum of 2 evaluable patients at each dose level for determination of MTD/Recommended Phase 2 dose (RP2D) of the combination nivolumab plus ipilimumab. Up to 6 additional patients with relapsed/refractory solid tumors without restrictions on heme evaluability may be enrolled at the RP2D determined in Part A and Part C to acquire PK data in a representative number of young patients (i.e. patients < 12 years old) at the MTD/RP2D in each Part. Once the dose-escalation portion of Part A is completed, cohorts that are open concurrently for eligible patients (including Parts B and C and potential PK expansion cohorts) may be selected at the treating physician's discretion pending slot availability.

The single-agent recommended Phase 2 dose of Part A was determined to be 3 mg/kg nivolumab.

The recommended Phase 2 dose of nivolumab in combination with ipilimumab from Part C was determined to be 3 mg/kg nivolumab and 1 mg/kg ipilimumab.

In the event a cohort in a given disease group in Part B is completed after Stage 1, a corresponding cohort in the same disease group will open for select disease types in Part D at the RP2D determined in Part C.

A minimum of 4 patients will be enrolled in Part A, and a maximum of 36 patients are possible. A maximum of 36 patients could occur in the unlikely scenario that each dose level is expanded to 12 patients per [Section 11.2.2](#), and a 20% inevaluable rate occurs. A minimum of 2 patients will be enrolled in Part C, and a maximum of 36 patients is possible similar to Part A. Review of the enrollment rate into previous COG new agent studies

indicates that 1-2 patients per month are available, which will permit completion of Part A within 11-22 months and Part C within 14-29 months.

Review of patient accrual onto recent Phase 2 solid tumor studies indicates the following entry rates for the various tumors under study can be achieved for Parts B, D and E:

Disease Group/Part	Patients/ Year
Neuroblastoma	10-12
Osteosarcoma	10-12
Rhabdomyosarcoma	8-10
Ewing Sarcoma	10-12
Hodgkin Lymphoma	10-12
Non-Hodgkin Lymphoma	10-12
Melanoma	3-4

A minimum of 10 evaluable patients per disease group will be enrolled in Parts B1-B6 and B8 and Parts D1-6. A maximum 22 per disease group will be enrolled in these cohorts. A non-statistical access cohort for the rare diagnosis of melanoma (Part B7) will remain open to enrollment until Parts B1-B6, B8 and Parts D1-6 are complete. If at any time after enrollment of three patients, cycle 1 DLT occurs in  $\geq 33\%$  in the melanoma cohort, enrollment to that cohort will be closed. There will be no required minimum or maximum accrual limits for Part B7; however, given the accrual rate of 3-4 patients/year a minimum of 0 evaluable patients and a maximum of 16 patients is anticipated to enroll in this disease group assuming the maximum study duration of 4 years. The maximum enrollment assumes a 10% inevaluable rate. Therefore, a minimum of 60 patients and a maximum of 170 patients will be enrolled in Part B. A maximum of 110 patients will be enrolled in Part D.

As cohort D5 investigates the combination of nivolumab and ipilimumab in patients who may be post-allogeneic BMT, if at any time after 3 enrollments, acute or chronic GVHD requiring systemic immunosuppression occurs in  $\geq 33\%$  of patients, the strata will be closed to accrual.

A minimum of 6 children  $< 12$  years of age and at least 6 children  $\geq 12$  years of age will be evaluated for tolerability and systemic exposure of single agent nivolumab RP2D in Parts A and B. If less than 6 patients  $< 12$  years of age are enrolled upon completion of accrual to Part B, additional children (any histology) will be added to Part A studied to reach the 6 patient minimum.

Update: As of Amendment #8 a total of 132 patients have been enrolled:

Part A: 13 patients

Part B: B1: 10 patients

B2: 10 patients

B3: 11 patients

B4: 10 patients

B5: 12 patients

B6: 10 patients

B7: 1 patient

B8: 8 patients

Part C: 18 patients

Part D: D2: 10 patients

D3: 10 patients

D4: 9 patients

A total 132 patients have enrolled into ADVL1412 to date. A minimum of 3 evaluable patients will be enrolled in Part E, and a maximum of 23 patients will be enrolled overall. The maximum enrollment assumes a 10% inevaluable rate, and this part of the study is anticipated to be completed within 2-23 months. Therefore, the maximum number of patients for the entire study is expected to be 155 with amendment 8, and this entire protocol will have been completed within 5.5 years.

## 11.2 Definitions

### 11.2.1 Evaluable For Adverse Events

For all parts of the study, any patient who receives at least one dose of the study drug(s) and who experiences a dose-limiting toxicity is considered evaluable for Adverse Events. In addition, for the dose-escalation portions (Parts A and C), during Cycle 1, patients must have the appropriate toxicity monitoring studies performed to be considered evaluable for dose limiting toxicity. In Parts A and C, patients who do not have DLT and do not receive at least 85% of the prescribed dose within the first 28 days (the DLT observation period) for reasons other than toxicities (e.g. progressive disease) will not be considered evaluable for toxicity and will be replaced.

### 11.2.2 Maximum Tolerated Dose

- The MTD will be the maximum dose at which fewer than one-third of patients experience DLT (See [Section 5.4](#)) during Cycle 1 of therapy.
- In the unlikely event that two DLTs observed out of 6 evaluable patients are different classes of Adverse Effects (e.g. hepatotoxicity and myelosuppression), AND all of the following conditions are met, expansion of the cohort to 12 patients will be considered:
  - One of the DLTs does not appear to be dose-related
  - The Adverse Effects are readily reversible
  - The study chair, DVL statistician, DVL committee chair or vice chair, and IND sponsor all agree that expansion of the cohort is acceptable

If fewer than 1/3 of patients in the expanded cohort experience dose-limiting toxicities, the dose escalation can proceed.

- The DLTs observed in the pharmacokinetic (PK) expansion cohort will be counted towards the total number of DLTs observed at the MTD during the dose escalation portion of the study. If  $\geq 1/3$  of the cohort of patients at the MTD (during the dose escalation plus the PK expansion) experience DLT then the MTD will be exceeded.

### 11.2.3 Evaluability for Response

Any patient who is enrolled who meets eligibility criteria for Parts B, D or E and receives at least one dose of protocol therapy will be considered evaluable for response provided: (1) the patient demonstrates progressive disease or death while on protocol therapy (note: if the institutional investigator determines that the

patient has progressed based on clinical or laboratory evidence, he/she may opt not to confirm this finding radiographically); or (2) the patient is observed on protocol therapy for at least one cycle and the tumor is not removed surgically prior to the time complete response or partial response is confirmed, or (3) the patient demonstrates a complete or partial response as confirmed according to protocol criteria. Patients who demonstrate a complete or partial response confirmed by central review will be considered to have experienced a response for the application of the rule given in Section 11.4. Two objective status determinations are required to confirm best response ([Section 12.6](#)). All other patients will be considered non-responders. All patients considered to have a response (CR or PR) must have imaging studies reviewed centrally at the COG. Centers will be notified by the COG about requests for scans of patients with stable disease. See [Section 8.2](#) regarding image submission instructions. The central review by COG will be provided as the final reviewed assessment of response when such becomes available. Patients inevaluable for response will be considered for replacement.

### 11.3 Determination of Recommended Phase 2 Dose for Nivolumab as a Single Agent (Part A):

- Part A will evaluate a single dose level (3 mg/kg). If 1 or fewer of 6 evaluable patients experience DLT and at least 5/6 of patients achieve a Cmin of at least 10 mcg/ml, the 3 mg/kg dose level will be the RP2D and we will conclude that children are not experiencing significantly less exposure than adults treated at the same dose. If however, < 5 of 6 patients achieve a Cmin of at least 10 mcg/ml, consideration will be given to a protocol amendment to test a higher dose level in Part A. Note that Cmin levels > 30 mcg/ml will not, in and of itself result in a change in protocol design, unless excess toxicity is observed.
- If 2 or more of the 6 patients experience DLT at the 3 mg/kg dose level, then the MTD has been exceeded and the 1 mg/kg dose level will be evaluated. If 1 or fewer of 6 patients experience DLT at the 1 mg/kg dose level and at least 5/6 of patients achieve a Cmin of at least 10 mcg/ml, then this dose level will be the RP2D. Once the RP2D for nivolumab as a single agent is determined, Part B and Part C will open simultaneously.

Update: The single-agent recommended Phase 2 dose of Part A was determined to be 3 mg/kg nivolumab.

### 11.4 Phase 2 Evaluation of Nivolumab (for Part B):

#### Study Design

The best response of disease to nivolumab will be examined separately for each of the tumor strata: neuroblastoma, osteosarcoma, rhabdomyosarcoma, ewing sarcoma, Hodgkin lymphoma, and non-Hodgkin lymphoma with the goal of enrolling at least evaluable 10 patients per tumor type. Given the activity seen in adult patients with melanoma, an additional non-statistical cohort for patients with unresectable, metastatic, relapsed or refractory melanoma will be open to accrual as Part B7 to preliminarily define the antitumor effects of nivolumab within the confines of a phase 1/2 study and will remain open for enrollment until Parts B1-B6, B8 are complete. Given the rarity of the disease in the pediatric population the study will not remain open to complete this cohort if all other strata have completed accrual. If at any time after enrollment of three patients, cycle 1 DLT occurs in  $\geq$

33% in the melanoma cohort, enrollment to that cohort will be closed. If at least 12 patients are treated at Part B7, evaluation of accrual rate and toxicities may be discussed with the sponsor to determine if any changes in study design are required. The following Simon's optimal two stage design will be used for Parts B1-B6, B8.

	Cumulative Number of Responses	Decision
Stage 1: Enter 10 patients	0	Terminate the stratum: agent ineffective
	1 or more	Inconclusive result, continue stratum (proceed to stage 2)
Stage 2: Enter 10 additional patients	2 or less	Terminate the stratum: agent ineffective
	3 or more	Terminate the stratum: agent effective

In the event that a cohort in a given disease group in Part B is completed after Stage 1 because no responses are observed, a cohort in the same disease group will open to up to 10 evaluable patients in Part D, at the RP2D of nivolumab in combination with ipilimumab as determined in Part C: 3 mg/kg nivolumab and 1 mg/kg ipilimumab (See [Section 11.6](#)).

Nivolumab will not be considered of sufficient interest for further evaluation in a disease category if the true response rate is 5% and of sufficient activity if the true response rate is 25%. If nivolumab has a true response rate of 5%, the rule described above will identify it of sufficient activity for further study with probability 0.07 (type I error), and the trial will have an expected sample size of 14 with 60% probability of early termination. If nivolumab has a true response rate of 25%, the rule described above will identify it of sufficient activity for further study with probability 0.88 (power against the alternative hypothesis  $P = 0.25$ ).

Children with a target diagnosis and measurable or MIBG evaluable disease who are enrolled on Part A and receive the RP2D will be considered evaluable for disease response in Part B.

If cycle 1 DLT occurs in  $\geq 33\%$  of evaluable patients in a cohort of Part B with at least 3 evaluable patients, the maximum tolerated dose will have been exceeded in this tumor type and the cohort will be closed to further enrollment.

Response in all patients with solid tumors will be determined according to RECIST as defined in the protocol as either complete response (CR), partial response (PR), stable disease (SD) or progressive disease (PD), or as described in [Section 12.0](#) for other categories of responses assessment, and reported as final results. A report on the efficacy assessment will be posted on the completed disease stratum as part of the semi-annual study committee meeting book report.

Method of Analysis

Response criteria are described in [Section 12.0](#). Response rates will be calculated separately for each of the tumor strata as the percent of patients whose best response is a CR or PR and confidence intervals will be constructed according to the method of Chang. A responder is defined as a patient who achieves a best confirmed response (as defined in [Section 12.6](#)) of PR or CR on the study and includes pseudo-progressive disease. Response is defined relative to baseline disease.

**11.5 Dose Escalation and Determination of Recommended Phase 2 Dose for Nivolumab plus Ipilimumab (Part C):**

The rolling six phase 1 trial design will be used for the conduct of Part C of this study. Two to six patients can be concurrently enrolled onto a dose level, dependent upon (1) the number of patients enrolled at the current dose level, (2) the number of patients who have experienced DLT at the current dose level, and (3) the number of patients entered but with tolerability data pending at the current dose level. Accrual is suspended when a cohort of six has enrolled or when the study endpoints have been met.

Dose level assignment is based on the number of participants currently enrolled in the cohort, the number of DLTs observed, and the number of participants at risk for developing a DLT (i.e., participants enrolled but who are not yet assessable for toxicity). For example, when three participants are enrolled onto a dose cohort, if toxicity data is available for all three when the fourth participant entered and there are no DLTs, the dose is escalated and the fourth participant is enrolled to the subsequent dose level. If data is not yet available for one or more of the first three participants and no DLT has been observed, or if one DLT has been observed, the new participant is entered at the same dose level. Lastly, if two or more DLTs have been observed, the dose level is de-escalated. This process is repeated for participants five and six. In place of suspending accrual after every three participants, accrual is only suspended when a cohort of six is filled. When participants are inevaluable for toxicity, they are replaced with the next available participant if escalation or de-escalation rules have not been fulfilled at the time the next available participant is enrolled onto the study.

The following table provides the decision rules for enrolling a patient at (i) the current dose level (ii) at an escalated dose level, (iii) at a de-escalated dose level, or whether the study is suspended to accrual:

# Pts Enrolled	# Pts with DLT	# Pts without DLT	# Pts with Data Pending	Decision
2	0 or 1	0, 1 or 2	0, 1 or 2	Same dose level
2	2	0	0	De-escalate*
3	0	0, 1 or 2	1, 2 or 3	Same dose level
3	1	0, 1 or 2	0, 1 or 2	Same dose level
3	0	3	0	Escalate**
3	≥ 2	0 or 1	0 or 1	De-escalate*
4	0	0, 1, 2 or 3	1, 2, 3 or 4	Same dose level
4	1	0, 1, 2 or 3	0, 1, 2 or 3	Same dose level
4	0	4	0	Escalate**
4	≥ 2	0, 1 or 2	0, 1 or 2	De-escalate*
5	0	0, 1, 2, 3 or 4	1, 2, 3, 4 or 5	Same dose level

5	1	0, 1, 2, 3 or 4	0, 1, 2, 3 or 4	Same dose level
5	0	5	0	Escalate**
5	≥2	0, 1, 2 or 3	0, 1, 2 or 3	De-escalate*
6	0	0, 1, 2, 3, or 4	2, 3, 4, 5 or 6	Suspend
6	1	0, 1, 2, 3 or 4	0, 1, 2, 3 or 4	Suspend
6	0 or 1	5 or 6	0 or 1	Escalate**
6	≥2	0, 1, 2, 3 or 4	0, 1, 2, 3 or 4	De-escalate*

\* If six patients already entered at next lower dose level, the MTD has been defined. If the lowest dose level is not tolerated, that part will close to accrual and discussed with sponsor.

\*\*If final dose level has been reached, the recommended dose has been reached.

If two or more of a cohort of up to six patients experience DLT at a given dose level, then the MTD has been exceeded and dose escalation will be stopped (see [Section 11.2.2](#) for exception to rule).

In addition to determination of the MTD, a descriptive summary of all toxicities will be reported.

### 11.6 Phase 2 Evaluation of Nivolumab (3 mg/kg) in Combination with Ipilimumab (1 mg/kg) (for Part D):

In the event that a cohort in a given disease group in Part B is completed after Stage 1 because no responses are observed, a corresponding cohort will open in the same disease group for select disease types to an initial cohort of up to 10 evaluable patients in Part D, at the RP2D of nivolumab in combination with ipilimumab as determined in Part C: 3 mg/kg nivolumab and 1 mg/kg ipilimumab.

#### 11.6.1 Study Design

The best response of disease to nivolumab in combination with ipilimumab will be examined separately for each of the tumor strata that are expanded from Part B. The following Simon's optimal two stage design will be used for Parts D1-6.

	Cumulative Number of Responses	Decision
Stage 1: Enter 10 patients	0	Terminate the stratum: agent ineffective
	1 or more	Inconclusive result, continue stratum (proceed to stage 2)
Stage 2: Enter 10 additional patients	2 or less	Terminate the stratum: agent ineffective
	3 or more	Terminate the stratum: agent effective

Nivolumab in combination with ipilimumab will not be considered of sufficient interest for further evaluation in a disease category if the true response rate is 5% and of sufficient activity if the true response rate is 25%. If nivolumab in combination with ipilimumab has a true response rate of 5%, the rule described above will identify it of sufficient activity for further study with probability 0.07 (type I error), and the trial will have an expected sample size of 14 with 60% probability of early termination. If nivolumab in combination with ipilimumab has a true response rate of 25%, the rule described above will identify it of sufficient activity for further study with probability 0.88 (power against the alternative hypothesis  $P = 0.25$ ).

Children with a target diagnosis and measurable or MIBG evaluable disease who are enrolled on Part C and receive the RP2D will be considered evaluable for disease response in Part D. The number of patients needed to evaluate any cohort in part D would therefore be reduced by the number of patients treated and evaluable for response in part C,

If cycle 1 DLT occurs in  $\geq 33\%$  of evaluable patients in a cohort of Part D with at least 3 evaluable patients, the maximum tolerated dose will have been exceeded in this tumor type and the cohort will be closed to further enrollment.

Response in all patients with solid tumors will be determined according to RECIST as defined in the protocol as either complete response (CR), partial response (PR), stable disease (SD) or progressive disease (PD), or as described in [Section 12.0](#) for other categories of responses assessment, and reported as final results. A report on the efficacy assessment will be posted on the completed disease stratum as part of the semi-annual study committee meeting book report.

Method of Analysis

Response criteria are described in [Section 12.0](#). Response rates will be calculated separately for each of the tumor strata as the percent of patients whose best response is a CR or PR and confidence intervals will be constructed according to the method of Chang. A responder is defined as a patient who achieves a best confirmed response (as defined in [Section 12.6](#)) of PR or CR on the study and includes pseudo-progressive disease. Response is defined relative to baseline disease.

**11.7 Phase 2 Evaluation of Nivolumab (1 mg/kg) in Combination with Ipilimumab (3 mg/kg) (for Part E):**

**11.7.1 Study Design**

The Simon’s optimal two stage design will be used for Part E to assess response in rhabdomyosarcoma (E3) and Ewing/Peripheral PNET pediatric patients (E4). All patients enrolled into either E3 or E4 will be combined for assessment of response and toxicity. Assuming that the study does not stop early for dose limiting toxicity, a total of 10 response-evaluable patients will be enrolled into Stage 1. This will include at least 4 patients each in parts E3 and E4. If at least 1 response is observed among 10 evaluable patients, then stage 2 will open for enrollment. A total of 10 more response-evaluable patients will then be enrolled into Stage 2 including at least 4 more patients each in parts E3 and E4. Otherwise, the study will close with stage 1 and the study will conclude that the agent does not elicit sufficient response.

The following Simon’s optimal two-stage design will be used to assess response in Part E.

	Cumulative Number of Responses	Decision
Stage 1: Enter 10 patients	0	Terminate the stratum: agent ineffective
	1 or more	Inconclusive result, continue stratum

		(proceed to stage 2)
Stage 2: Enter 10 additional patients	2 or less	Terminate the stratum: agent ineffective
	3 or more	Terminate the stratum: agent effective

The combination of Nivolumab (1 mg/kg) and Ipilimumab (3mg/kg) will not be considered of sufficient interest for further evaluation among Rhabdomyosarcoma and Ewing/Peripheral PNET patients if the true response rate is  $\leq 5\%$  and of sufficient activity if the true response rate is  $\geq 25\%$ . If this combination has a true response rate of 5%, the rule described above will identify it of sufficient activity for further study with probability 0.07 (type I error), and the trial will have an expected sample size of 14 with 60% probability of early termination. If the combination has a true response rate of 25%, the rule described above will identify it of sufficient activity for further study with probability 0.88 (power against the alternative hypothesis  $P = 0.25$ ). A maximum of 23 patients will be enrolled into Part E allowing for 10% inevaluability.

If at least one Cycle 1 dose limiting toxicity occurs among the first 10 patients or 4 patients with dose limiting toxicities among 20 patients, then the study will close and conclude that the dose level is too toxic. This rule will provide  $\geq 89\%$  power to terminate the study in stage 1 and  $\geq 90\%$  power overall to terminate the study due to excessive Cycle 1 toxicity when the true cycle 1 toxicity is  $\geq 20\%$ . Otherwise, the study will continue per the 10+10 Simon two-stage design. The overall type 1 error rate for this rule is 40% if the true Cycle 1 toxicity is 0.05 and 66% if the true toxicity is 0.10.

All grade 3, 4, and 5 toxicity attributed to protocol therapy will reviewed weekly by the study committee and discussed during the scheduled monthly sponsor calls in order to determine the need for any changes. Consideration to open the second stage will be discussed by all approved parties (i.e. DSMC, NCI) following the release of the aggregated data for all events.

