The response rate of nivolumab (3 mg/kg) alone and nivolumab (3 mg/kg) in combination with ipilimumab (1 mg/kg) has been low in this pediatric study providing rationale to study a different dose combination in Part E. Part D (nivolumab 3 mg/kg and ipilimumab 1 mg/kg) will close to accrual with this amendment. To determine if the increased dose of ipilimumab demonstrates efficacy in pediatric solid tumor histologies, we will launch Part E to look for a signal of efficacy with the regimen of ipilimumab 3 mg/kg plus nivolumab 1 mg/kg. Part E will look for evidence of a response in patients with rhabdomyosarcoma (E3) or Ewing sarcoma/Peripheral PNET (E4). A 10+10 Simon two-stage design will be used for Part E. All patients enrolled into Parts E3 or E4 will be combined into a single cohort for evaluation of response and toxicity. Assuming that the study does not close due to toxicity, enrollment will include at least 4 rhabdomyosarcoma patients and 4 Ewing sarcoma/Peripheral PNET patients in stage 1. If the study continues to stage 2, then the overall study will include at least 8 patients in each of the two disease cohorts. If at least one Cycle 1 dose limiting toxicity occurs among the first 10 patients or 4 dose limiting toxicities among 20 patients, then the study will close and conclude that the dose level is too toxic. Otherwise, the study will plan to enroll a total of 20 response-evaluable pediatric patients.

Ipilimumab at 3 mg/kg as single agent has been tested in pediatric patients and found to be tolerable. Data from Part A and Part C of this study have demonstrated tolerability and safety of both single agent nivolumab at 3 mg/kg, also when used in combination with 1 mg/kg of ipilimumab. Thus, we anticipate the combination regimen of ipilimumab 3 mg/kg and nivolumab 1 mg/kg to be well tolerated.

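### Part E's expected N of 14, 60% early termination and power of 0.88 describe the response rule alone; with the toxicity rule also applied, the chance of finding a 25% response rate active is about 0.53 at 5% DLT and 0.30 at 10% DLT

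*Combined protocol and SAP*

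**What the plan says.** Section 11.7.1 uses a 10+10 two-stage rule for response. Part E stops after 10 patients if there is no response, and the regimen is called effective if there are 3 or more responses among 20. The inactive and active response rates are 5% and 25%. The stated type I error is 0.07, and the power is given in these words: "combination has a true response rate of 25%, the rule described above will identify it of sufficient activity for further study with probability 0.88". For the 5% response rate the text adds that "the trial will have an expected sample size of 14 with 60% probability of early termination".

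Rhabdomyosarcoma (E3) and Ewing sarcoma/peripheral PNET (E4) form one cohort for both purposes: "All patients enrolled into either E3 or E4 will be combined for assessment of response and toxicity".

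The same section then gives a toxicity rule, which closes the study and declares the dose level too toxic: "If at least one Cycle 1 dose limiting toxicity occurs among the first 10 patients or 4 patients with dose limiting toxicities" among 20. After this rule it says: "Otherwise, the study will continue per the 10+10 Simon two-stage design". The closure probabilities are stated separately: "The overall type 1 error rate for this rule is 40% if the true Cycle 1 toxicity is 0.05 and 66"% if it is 0.10. At a true rate of 20% or more they are at least 89% in stage 1 and at least 90% overall.

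Enrolment is qualified in two places. Section 11.7.1 says "Assuming that the study does not stop early for dose limiting toxicity, a total of 10 response-evaluable patients will be enrolled into Stage 1", and Section 2.11 says "Assuming that the study does not close due to toxicity, enrollment will include at least 4 rhabdomyosarcoma patients".

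**The concern.** Part E can conclude activity only if it passes both rules, and both act on the same pooled patients. Each rule has its own operating characteristics in the text, but the design that will be run is the combination, and nothing is stated for it. The sentence on sample size and early termination goes further, because its subject is the trial. At any non-zero DLT rate the trial does not have those two properties.

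Part E is the only part not marked as completed in Section 5.1, so its power statement is the one still in use for planning. Section 2.11 expects the regimen to be well tolerated, and Section 2.5 reports 1 DLT among 12 evaluable patients at the Part C recommended dose. That was a different dose combination and does not establish the rate in Part E, but it shows that single-figure DLT rates are not far-fetched. A reader who takes 0.88 as the chance that Part E detects a 25% response rate would be well off the mark at such rates, and might read a closure after one DLT as a failure to show activity.

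**Working it through.** **Inputs, all from Section 11.7.1.** Response rule: continue if there is at least 1 response in 10; active if there are at least 3 in 20. Response rates p = 0.05 and 0.25. Toxicity rule: close at 1 or more DLT in the first 10, or at 4 among 20. DLT rates q = 0.05 and 0.10 (the rates for which the plan gives a type 1 error) and 0.20 (the rate for which it gives power to close).

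**Step 1: response rule alone.** P(active) = P(Bin(20,p) ≥ 3) − (1−p)^10 × P(Bin(10,p) ≥ 3).

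- p = 0.25: 0.9087 − 0.0563 × 0.4744 = 0.8820 (stated 0.88).
- p = 0.05: 0.0755 − 0.5987 × 0.0115 = 0.0686 (stated 0.07).
- Early termination at p = 0.05: 0.95^10 = 0.5987 (stated 60%).
- Expected N at p = 0.05: 10 + 10 × (1 − 0.5987) = 14.01 (stated 14).

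All four stated figures are reproduced with no toxicity rule in the calculation.

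**Step 2: toxicity rule alone.** The probability of not closing is c(q) = (1−q)^10 × P(Bin(10,q) ≤ 3).

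| q | (1−q)^10 | P(Bin(10,q) ≤ 3) | c(q) | Closure, 1 − c(q) | Stated closure |
|---|---|---|---|---|---|
| 0.05 | 0.5987 | 0.9990 | 0.5981 | 0.402 | 40% |
| 0.10 | 0.3487 | 0.9872 | 0.3442 | 0.656 | 66% |
| 0.20 | 0.1074 | 0.8791 | 0.0944 | 0.906 | at least 90% |

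Stage 1 closure at q = 0.20 is 1 − 0.1074 = 0.893 (stated at least 89%). These figures are reproduced too, so both rules have been read as intended.

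**Step 3: both rules.** Assume that DLT and response are independent and that the same 10+10 patients count for both. Then P(conclude activity) = P(active) × c(q).

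| | Response rule alone | 5% DLT | 10% DLT |
|---|---|---|---|
| P(conclude activity), p = 0.25 | 0.88 | 0.8820 × 0.5981 = 0.528 | 0.8820 × 0.3442 = 0.304 |
| P(conclude activity), p = 0.05 | 0.07 | 0.0686 × 0.5981 = 0.041 | 0.0686 × 0.3442 = 0.024 |
| P(end by stage 1), p = 0.05 | 0.60 | 1 − 0.4013 × 0.5987 = 0.760 | 1 − 0.4013 × 0.3487 = 0.860 |
| Expected N, p = 0.05 | 14 | at most 10 + 10 × 0.240 = 12.4 | at most 10 + 10 × 0.140 = 11.4 |

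The expected N values are ceilings, because they let each stage fill before closure takes effect.

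**Step 4: sensitivity to the two assumptions.** Exact enumeration at p = 0.25 was run with the joint probability of response and DLT in one patient set to its smallest value (0) and its largest (the smaller of p and q). P(conclude activity) is then 0.536 and 0.495 at 5% DLT, and 0.314 and 0.255 at 10%. The documents do not establish the direction of any association. If patients who are inevaluable for response also count for toxicity, the probabilities fall further. With 11 patients per stage counted for toxicity, as an illustration, the results are 0.8820 × 0.5688 × 0.9984 = 0.50 and 0.8820 × 0.3138 × 0.9815 = 0.27.

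**Step 5: where the loss arises.** At p = 0.25 the chance of opening stage 2 is 0.9437 × 0.5987 = 0.565 at 5% DLT and 0.9437 × 0.3487 = 0.329 at 10%, against 0.944 under the response rule alone. Once stage 2 is open, the chance of concluding activity is (0.8820/0.9437) × 0.9990 = 0.93 and (0.8820/0.9437) × 0.9872 = 0.92. Almost all of the loss comes from stage 1 closure.

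**The case against.** The strongest reply is that nothing here is miscalculated or hidden. The power and type I error are expressly tied to the response rule set out just before them. The toxicity closure probabilities follow in the next paragraph, and the enrolment text in Sections 11.7.1 and 2.11 is conditional on no toxicity stop. A careful reader can multiply 0.88 by 0.60 or by 0.34. Parts B and D use the same power wording beside a separate DLT closure rule, again without a joint figure, so separate reporting is this protocol's habit. The false-positive risk for activity only falls.

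Much of this stands. A reader might infer that 0.88 or 0.07 is an arithmetic error; the documents do not support that, since both reproduce for the rule they describe. A reader might also infer that the low probability at 20% DLT (0.8820 × 0.0944 = 0.08) is lost power. It is not, because closure at that rate is what the toxicity rule is for. Nor does the point bear on the decision to open stage 2, given the 0.93 and 0.92 above.

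What remains is narrower. The conditional clauses qualify enrolment, not the power statement, and they give no size for the loss. The sentence on expected N and early termination makes the trial its subject. The multiplication also needs assumptions about independence and about who is counted, which the plan does not state.

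**Conclusion.** The concern holds as a gap in the stated operating characteristics of Part E, not as an arithmetic error. Section 11.7.1 attributes an expected N of 14 and 60% early termination to the trial, and gives no overall probability of concluding activity, although a second rule closes the same patients. Overall, a 25% response rate leads to a conclusion of activity with probability about 0.53 at 5% DLT and 0.30 at 10% DLT. The plan itself classes closure at those two rates as type 1 error.

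These central figures rest on independence of DLT and response and on identical toxicity and response-evaluable sets. Dependence does not overturn the conclusion: its extremes span 0.50–0.54 and 0.26–0.31. Counting additional patients for toxicity would only lower the figures. No view is taken here on whether either rule is the right one.

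**What to change.** In Section 11.7.1, change the subject of the clause on expected sample size and early termination from the trial to the response rule alone, ignoring closure for toxicity. After the sentence giving 0.88, add:

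> With the toxicity rule below also applied, and assuming that DLT and response are independent and that the same patients are evaluable for both, the overall probability of concluding sufficient activity at true Cycle 1 DLT rates of 5% and 10% is about 0.53 and 0.30 if the true response rate is 25% (0.50–0.54 and 0.26–0.31 under extreme dependence), and about 0.04 and 0.02 if it is 5%. At a 5% response rate, early termination is then about 76% and 86%, and expected N is at most about 12.4 and 11.4.

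The sample size, both rules and the stated toxicity closure figures stay unchanged. The cost is one reworded clause and one short addition, and a less favourable overall power on the page.

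Section 11.1 also gives two different minimum enrolments for Part E (2 and 3) and two durations (1–23 and 2–23 months). Those are separate clerical items and do not support this point.
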